12. SAFETY

12.1. Adverse Events

Adverse events will be summarized separately for those occurring in the study eye, in the fellow eye, and non-ocular events. For overall AE incidence summary, one table for ocular AEs (study eye and fellow eye combined) will be reported. In this table, each subject will be counted only once in each summary category, to avoid correlated data. However, the results should be interpreted with caution because fellow eyes are selective samples by study design. Regardless of whether the fellow eye is treated or not, all AEs reported for the fellow eye will be included for the safety analysis. AEs marked as 'Both Eyes (OU)' from the AE CRF page will be summarized both for study eye and fellow eye.

All AE verbatim terms will be coded using Medical Dictionary for Regulatory Activities (MedDRA) version 23.0 Update. Terms will be coded to the full MedDRA hierarchy, but the system organ class (SOC) and preferred term (PT) will be of primary interest for the analysis.

Treatment emergent adverse events (TEAEs) are defined as AEs that first occurred or worsened on or after the date of first administration of study drug. If missing dates or time prevent a clear determination as to whether the AE is treatment emergent, the AE will be regarded as a TEAE.

While all AEs will be summarized, the main AE summaries will be restricted to TEAEs only. Treatment emergent adverse events will be summarized descriptively. For the summary of TEAEs, if a subject experienced the same AE multiple times, this will only be counted once for the purpose of counting the number of patients experiencing that AE. Summary tables will include the number of subjects (%) experiencing an AE and the number of AEs.

The TEAE summaries will include:

- Overall Summary of Subjects with at Least One Adverse Event
- Summary of TEAEs by SOC and PT
- Summary of TEAEs with an Incidence $\geq 5\%$ by SOC and PT
- Summary of Serious TEAEs by SOC and PT

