Subjects will be randomly assigned to receive treatment twice daily (BID) for 84 days (Days 0 to 83). Subjects will receive instructions for dosing at home and for completing a dosing diary during the study dosing period (Visit 2 [Day 0] to Visit 6 [Day 84]).

Subjects (or their caregivers) will be instructed to store the study drug at room temperature (15°- 25°C; 59° - 77°F), to protect the study drug from light and to not freeze the study drug, as well as to instill one dose BID (preferably 8-12 hours apart) in the study eye on Days 0 to 83.

If deemed necessary by the investigator, study drug may also be instilled in the fellow eye. If the investigator deems that the fellow eye should also be treated, then the same unit-dose container used to dose the study eye should be used to deliver a dose to the fellow eye. If both eyes are treated with study drug, all study assessments will be performed on the treated eyes, but the fellow eye will only be analyzed for safety while the study eye will be analyzed for safety and efficacy.

During the dosing phase (Day 0 to Day 83), subjects will self-instill (or will have study drug instilled by the subject's caregiver) one drop of study drug BID on the study eye for 84 days. Subjects will then be followed for approximately 2 weeks during the evaluation phase (Day 84 to Day 98).

There will be 7 study visits for full study participation: 1 visit during the screening phase, 4 visits (Day 0, Day 7, Day 30, and Day 60) during the dosing phase, and 2 visits (Day 84 and Day 98) during the post-treatment evaluation phase.

Subjects' safety will be evaluated throughout the study. The safety parameters to be assessed are the incidence, severity, and relationship of adverse events (AEs) and serious adverse events (SAEs), discontinuations due to AEs, changes in visual acuity (VA) and intraocular pressure (IOP), and biomicroscopic and ophthalmoscopic findings in treated eyes.

Efficacy will be assessed as follows:

Primary efficacy endpoint: University of North Carolina Dry Eye Management Scale (UNC DEMS)

A reduction of 10% in patient-reported DED symptoms and reduction of impact of symptoms on daily life at Day 84 as defined by the UNC DEMS with SURF-100 as compared to vehicle, 0.05% cyclosporine ophthalmic emulsion, and 5% lifitegrast ophthalmic solution.

Secondary efficacy endpoints:

1. Tear Break-up Time (TBUT)

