8. CLINICAL ASSESSMENTS/EXAMINATION PROCEDURES

Subject Completed Assessments:

UNC DEMS Questionnaire: The UNC DEMS will be completed by subjects at Visit 1 (Screening; Day -14 to Day 0) and only at Visit 2 (Day 0) if Visit 2 is >5 days following Visit 1. The UNC DEMS will also be completed by subjects at Visit 3 (Day 7) through Visit 7 (Day 98).

Dosing Diary with Drop Comfort Questionnaire: Subjects will be given a Dosing Diary with Drop Comfort Questionnaire to record study drug dose instillation dates and times for each dose, as well as to record their responses to the Drop Comfort Questionnaire every 7 days during the dosing period (Day 0 to Day 83).

Investigator Assessments:

Best-Corrected Visual Acuity (BCVA): BCVA will be performed in both eyes at Visit 1 (Screening; Day -14 to Day 0) and only at Visit 2 (Day 0) [prior to randomization] in both eyes if Visit 2 is >5 days following Visit 1. BCVA will also be performed in treated eyes at Visit 3 (Day 7) through Visit 7 (Day 98). Log of the minimum angle of resolution [logMAR] score using ETDRS [Early Treatment Diabetic Retinopathy Study] chart will be used to measure BCVA. Performing a pinhole test is allowed as long as its use remains consistent for the same subject throughout all study visits.

Biomicroscopy: Slit lamp biomicroscopy will be performed to observe the overall health of the eye, including the lid/lashes, conjunctiva, cornea, anterior chamber, iris, and lens. This will be performed in both eyes at Visit 1 (Screening; Day -14 to Day 0) and only at Visit 2 (Day 0) [prior to randomization] if Visit 2 is >5 days following Visit 1. Slit lamp biomicroscopy will also be performed in treated eyes at Visit 3 (Day 7) through Visit 7 (Day 98).

Ophthalmoscopy: An undilated ophthalmoscopy exam will be performed in both eyes at Visit 1 (Screening; Day -14 to Day 0) and in treated eyes at Visit 7 (Day 98).

Intraocular Pressure (IOP): IOP will be measured in both eyes at Visit 1 (Screening; Day -14 to Day 0) and only at Visit 2 (Day 0) [prior to randomization] if Visit 2 is >5 days following Visit 1. IOP will also be measured in treated eyes at Visit 3 (Day 7) through Visit 7 (Day 98).

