10.3. Analysis Populations

Safety Population: The safety population includes all randomized subjects who receive at least 1 dose of the study drug. Subjects in the safety population will be analyzed in the treatment group for the study drug they received.

Intent-to-Treat Population: The Intent-to-Treat (ITT) population includes all randomized subjects. Subjects in the ITT population will be analyzed in the treatment group to which they were assigned by the randomization schedule, regardless of which study drug they receive.

Per Protocol Population: The per-protocol (PP) population includes all subjects in the ITT population who have no significant protocol deviations during the study.

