10.5. Statistical Methods: General Considerations

All final statistical analyses will be performed after the study database has been locked, unmasked, and released for statistical analysis. All tables, statistical analyses, figures, and subject data listings will be generated using SAS® Version 9.4 or later (SAS Institute Inc., Cary, North Carolina, United States of America).

All data in the database will be presented in the data listings. Unless otherwise stated, all listings will be sorted by treatment group, subject number and assessment visit, as appropriate.

Unless otherwise stated, continuous variables will be summarized using descriptive statistics including number of non-missing observations (n), mean, standard deviation (SD), median, minimum and maximum values. The minimum and maximum values will be presented to the same number of decimal places as the eCRF or laboratory reported data; mean, SD, and median will be presented to one more decimal place than the source data.

Categorical variables will be summarized with frequency counts and percentages. The population size (N for sample size and n for available data) and the percentage (of available data) for each class of the variable will be presented. Percentages will be rounded to one decimal place, with the denominator being the number of patients in the relevant population, unless otherwise stated.

Only data from nominal protocol scheduled visits will be included in the summary tables. Data

from unscheduled visits will not be included in the summary tables but will be included in the figures and listings.

It should be noted that in this study the analysis unit is subject. When data from both eyes are available, data will not be pooled together for the analysis because eyes from the same subject are not independent samples. Statistical analysis generally requires independent samples. Each subject has a designated study eye as per the protocol. Therefore, separate analysis will be conducted for study eye and fellow eye as appropriate.

All confidence intervals (CIs) of the parameter estimates will be two-sided and at the significance level of 0.05 unless otherwise stated.

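### The fellow-eye adverse event percentage pools dosed and undosed fellow eyes over all safety subjects, so it is likely to understate the rate in dosed fellow eyes; Section 12.1 should split it by dosing status.

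*Combined protocol and SAP*

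**What the plan says.** Section 2 lets the investigator decide whether the fellow eye is dosed. It gives no criteria and no time by which the decision must be made. It adds: "If both eyes are treated with study drug, all study assessments will be performed on the treated eyes", with the fellow eye then analyzed for safety only.

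Section 8 schedules the ocular examinations after baseline in treated eyes only. This covers visual acuity, slit lamp, ophthalmoscopy, IOP, hyperemia, TBUT, staining and Schirmer. For the slit lamp it reads: "Slit lamp biomicroscopy will also be performed in treated eyes at Visit 3 (Day 7) through Visit 7 (Day 98").

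On reporting, Section 12.1 says: "Adverse events will be summarized separately for those occurring in the study eye, in the fellow eye, and non-ocular events". On which fellow-eye events count, it says: "Regardless of whether the fellow eye is treated or not, all AEs reported for the fellow eye will be included for the safety analysis". On what is shown, it says: "Summary tables will include the number of subjects (%) experiencing an AE and the number of AEs". None of these sentences gives a fellow-eye denominator. After describing the combined ocular table, the section also warns that fellow eyes are a selected group.

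The general rule for percentages is in Section 10.5: "with the denominator being the number of patients in the relevant population, unless otherwise stated". The same paragraph also refers to "the percentage (of available data) for each class of the variable will be presented". The population for AEs is set by subject, not by eye, in Section 10.3: "The safety population includes all randomized subjects who receive at least 1 dose of the study drug".

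**The concern.** Read together, these sections put two different kinds of eye into one percentage. A dosed fellow eye is exposed and examined at every post-baseline visit. An undosed fellow eye has no direct exposure and no scheduled examination. Some AE rules in Section 9 depend on an examination and are not limited to the study eye: new slit-lamp findings, IOP of 30 mmHg or higher, and ophthalmoscopy worsening. An undosed fellow eye has no scheduled examination that would detect these.

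The resulting percentage is not an event rate in exposed eyes, and it varies with how many fellow eyes were dosed. A reader of the table cannot correct for this, because Section 12.1 does not ask for the number of dosed fellow eyes per arm. Dosed fellow eyes are a second source of local safety data, and Section 6 says adverse reactions to topical ophthalmic MPA have not yet been established.

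**Working it through.** The plan states no fellow-eye rate or denominator count, so there is no figure to reproduce.

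**Inputs**
- Subjects per arm: 280 to 350 over 7 balanced groups (Section 2), so 280/7 = 40 to 350/7 = 50. The midpoint, 45, is used below.
- Share of fellow eyes dosed, *f*: not in the documents. Assumed 50% to 90%.
- Event rate in dosed fellow eyes, *r_d*: not in the documents. Assumed 10%. As a second example, 17% is the ocular burning figure that Section 6 gives for cyclosporine 0.05%.
- Recorded event rate in undosed fellow eyes, *r_u*: not in the documents. Assumed 0%, with 2% as a check.

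**1. Dilution.** Reported rate = *f* × *r_d* + (1 − *f*) × *r_u*.

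| *r_d* | *r_u* | *f* = 50% | *f* = 90% |
|---|---|---|---|
| 10% | 0% | 5.0% | 9.0% |
| 10% | 2% | 6.0% | 9.2% |
| 17% | 0% | 8.5% | 15.3% |
| 17% | 2% | 9.5% | 15.5% |

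With dosed fellow eyes as the denominator, the expected figure is 10% or 17% whatever the value of *f*.

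**2. The table of events with incidence of 5% or more.** If it is produced for fellow eyes and *r_u* = 0, a term enters only when *r_d* is at least 5%/*f*. That is 10% at *f* = 50% and 5.6% at *f* = 90%.

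**3. Effect on comparisons between arms.** The 95% chance range for the difference in dosed share between two arms of 45 is 1.96 × √(2*f*(1 − *f*)/45).
- *f* = 50%: 1.96 × √(0.50/45) = 0.207, about 21 points. The spurious difference in reported rate is 0.207 × 10% = 2.1 points, or 0.021 × 45 = 0.9 of a subject.
- *f* = 90%: 1.96 × √(0.18/45) = 0.124, about 12 points. The spurious difference is 0.124 × 10% = 1.2 points.

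For scale, the 95% sampling error on a single 10% rate with 45 subjects is 1.96 × √(0.10 × 0.90/45) = 0.088, about 9 points. The artefact between arms is small beside that. The understatement within each arm is the larger effect.

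**The case against.** The strongest reply is that the denominator is inferred. The sentence in Section 12.1 fixes which events count, not what they are divided by, and Section 10.5 mentions available data as well as the population. This is fair as far as it goes. But available data has no defined meaning for AEs in an eye with no scheduled examination, and Section 12.1 states no exception, so the population default is the natural reading. The ambiguity is itself a reason to state the denominator.

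Four stronger readings are tempting, and the documents do not support them.
- *Undosed fellow eyes cannot contribute events.* Subjects are asked about AEs at every visit (Section 8), and extra examinations are allowed (Sections 2 and 9). Detection is reduced, not zero.
- *The table could show a sizeable false difference between arms.* At a 10% rate, a 4-point difference needs a 40-point gap in dosing, such as 50% against 90%. That is 0.40/√(0.50/45) = 3.8 standard errors, and treatment is randomized and masked. A dosing decision made late could depend on response, since no timing is set, but nothing in the documents points to a gap of that size.
- *Harm in the steroid arms would be hidden.* Study-eye events have their own table, which is unaffected. The combined ocular table counts each subject once, so its subject denominator is correct. A term below 5% still appears in the full table by system organ class and preferred term.
- *Section 2 contradicts Section 12.1.* Section 2 says how a dosed fellow eye is analyzed. It does not say that events in undosed fellow eyes are left out.

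It is also true that a high dosed share is plausible, since inclusion criterion 6 (Section 4.1) requires a history of dry eye in both eyes. The understatement would then be slight. The plan's warning about selection is sound, but it neither changes the denominator nor gives the count needed to adjust for it.

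**Conclusion.** The point holds as a reporting weakness of modest size. As written, the fellow-eye percentage mixes dosed and undosed eyes and is likely to understate the rate in dosed fellow eyes. With an assumed 10% dosed-eye rate and no events in undosed eyes, the figure shown is 5.0% at 50% dosed and 9.0% at 90% dosed. The direction rests on fewer recorded events in undosed than in dosed fellow eyes. The size rests on a dosed share that the documents do not give. Between arms, chance imbalance in dosing accounts for about 2 points at most within the 95% range under the same assumptions. The efficacy analyses and the study-eye safety table are not touched.

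**What to change.** In Section 12.1, report fellow-eye treatment-emergent AEs in two parts:
- (a) fellow eyes that received at least one dose, with the number of such eyes in the arm as the denominator;
- (b) undosed fellow eyes, with their own denominator.

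Use the denominator in (a) for the table of events with incidence of 5% or more, where that table is produced for fellow eyes. Report the number of dosed fellow eyes per arm. No event is dropped, and the study-eye and combined ocular tables stay as they are.

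Where the date of the first fellow-eye dose is recorded, flag fellow-eye events that began before it. Otherwise keep the existing treatment-emergent definition. Section 8 describes diary entries of dose dates and times without mentioning the eye, so the documents do not show that this date is collected.

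The cost is SAP wording, a fellow-eye dosing flag, one extra table split and smaller denominators. At a 50% dosed share, an arm of 45 has about 0.5 × 45 = 22.5 dosed fellow eyes. The 95% half-width on a 10% rate is then 1.96 × √(0.09/22.5) = 0.124, about 12 points, against about 9 points with 45. The change should be made before unmasking.
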